Acoustic Radiation Force Impulse (ARFI) Imaging for Targeted Prostate Biopsy

Document Date: October 18, 2023

NCT04607135

Purpose of the Study

The objective of the proposed study is to evaluate the feasibility of a new ultrasonic acoustic radiation force impulse (ARFI) elasticity imaging system with a custom-designed transducer and biopsy guide to provide imaging guidance and targeting during prostate needle biopsy. This study will be conducted in two parts. Part 1 will evaluate a new, custom designed ultrasound transducer and needle guide in performing systematic transrectal ultrasound-guided prostate biopsies, as is the current standard-of-care. In addition to standard imaging, the new probe will be capable of ARFI measurements of tissue stiffness. Part 2 will evaluate the feasibility of targeted prostate biopsy guidance using ultrasound ARFI targeting as compared to ultrasound-MR fusion targeting in subjects electing to have ultrasound fusion-MR targeted biopsy procedures.

Background & Significance

Prostate cancer is the most common cancer and the second leading cause of cancer death for American men. For men harboring occult aggressive cancers, early diagnosis is essential for better treatment and increasing survival rate. Although the current screening techniques (prostate-specific antigen (PSA) blood testing and digital rectal examination (DRE)) are moderately sensitive but lack specificity for cancer screening, resulting diagnostic biopsies have significant shortcomings. Transrectal ultrasound is currently used to provide biopsy guidance only; however, it has poor sensitivity and specificity for prostate cancer. Without a good imaging technique to guide the needle biopsy in prostate glands, only about 25% of tests are positive for cancer in more than 1 million prostate biopsies performed each year; the false negative rates range from 25-45% based on the first-time biopsy. Although studies have shown more biopsy cores can increase diagnostic accuracy, prostate needle biopsy is an invasive procedure for the patient associated with both pain and risks, such as infection, hematuria (blood in the urine), urinary retention, hematochezia (blood during bowel movement), and hematospermia (blood in the semen). More biopsy cores mean higher risk for the patient. Thus, improved needle biopsy procedures guided by ARFI imaging would be of great clinical benefit.

Design & Procedures

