PART 1: The new ultrasound probe will be used in the same manner as current probes for standard-of-care prostate biopsy using systematic sampling with transrectal ultrasound (TRUS) guidance. In addition to B-mode images during the procedure, ARFI images will be acquired immediately before each needle insertion, after needle insertion, and following needle removal in each sampled image plane. The additional time required for ARFI measurements will be approximately 5-10 minutes.

PART 2: Three-dimensional ARFI images of the prostate will be acquired by sweeping the imaging plane through the prostate volume as in our current study of ARFI prostate imaging (Pro00006458), using the custom-designed ARFI-capable ultrasound probes. Image volume acquisition will take approximately 12 minutes, and not more than 20 minutes. Display of these images will be in real-time, and immediately following the volume acquisition, the most suspicious targets (up to 3) in the gland will be identified. The ultrasound probe will be positioned to image the target in plane and two-four biopsy cores will be acquired per target – with ARFI and B-mode image data acquired from each targeting procedure. The

ARFI ultrasound probe will be removed, and the standard ultrasound-MR fusion biopsy procedure will then proceed using the clinical ultrasound fusion-MR system. The additional time required to acquire the ARFI image volume and perform the ARFI-targeted biopsy cores is approximately 25-30 minutes

Selection of Subjects

PART 1: We will enroll patients scheduled for standard TRUS biopsy with suspected PCa.

PART 2: We will enroll patients with suspected PCa who are scheduled to undergo an ultrasound fusion-MR prostate biopsy.

Due to the nature of PCa, this study is open to men only; women and children are excluded. It is open to members of all racial and ethnic groups. Patients will be recruited by the treating physician or a healthcare provider known to the patient at the time of consultation.

Inclusion criteria:

PART 1: Men with suspected PCa based on suspicious PSA or DRE, or abnormal radiological finding scheduled for standard TRUS prostate biopsy;

PART 2: Men who are scheduled to undergo ultrasound fusion-MR prostate biopsy;

Men who are willing to participate in the study;

Subjects must freely sign informed consent to enroll in the study;

18 years or older

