For the second part of the study, we will test the hypothesis that ARFI guided targeted biopsy provides a higher PCa detection rate than that reported for systematic TRUS biopsy. We will also compare ARFI-targeted biopsy performance to that of MR-ultrasound fusion targeting by evaluating the biopsy cores obtained using each method with standard statistical tests to compare the length and grade of cancerous tissue in the cores. Biopsies will be scored for clinically significant disease (CSD) using the same clinical standard as for TRUS biopsy (e.g., percent PCa per/core, Gleason score, Gleason Grade Group) and yield of CSD (i.e., number of cores containing CSD/total number of cores) for each biopsy method. In addition, the spatial location of the targeted cores within the prostate will be compared between ARFI and Ultrasound-MR fusion. Assuming an ARFI imaging specificity for CSD of 70% (our preliminary data from Protocol Pro00006458 in patients receiving radical prostatectomy yielded 79% CSD from ARFI suspicious regions, and, 71% detection of all CSD present in the gland), and comparing to the systematic sampling TRUS PCa mean detection rate of 30% that has been well-established in the literature, inclusion of 35, 45, and 50 patients would achieve study powers of 80%, 90%, and 95%, respectively through a one-mean, one-sample equivalence test with a 30% testing margin and a standard deviation of up to 20% of the target ARFI imaging specificity. We plan to include 50 patients in this Part 2 study, plus 10 initial patients for early phase development and workflow integration (60 total in part 2).

Direct personal identifiers in study records will not be disclosed outside of Duke University Health System. For records disclosed outside of Duke, subjects will be assigned a unique code number.

Data & Safety Monitoring

The Principal Investigator, [name], will be responsible for monitoring the safety of these studies. As previously described, we do not anticipate any adverse events. However, in the event that adverse events occur, they will be immediately reported in detail in writing to the Duke University Medical Center's Institutional Review Board (IRB) in accordance with the re portable events policy.

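### The 70% planning value for Part 2 comes from radical prostatectomy patients and is not adjusted for enrolled men who have no cancer

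*Combined protocol and SAP*

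**What the plan says.** Data Analysis & Statistical Considerations gives the Part 2 hypothesis: "ARFI guided targeted biopsy provides a higher PCa detection rate than that reported for systematic TRUS biopsy". The sample size paragraph begins "Assuming an ARFI imaging specificity for CSD of 70" percent. It supports that value with two results from an earlier protocol. One is a yield by region: "our preliminary data from Protocol Pro00006458 in patients receiving radical prostatectomy yielded 79% CSD from ARFI suspicious regions". The other is the share of disease found: "71% detection of all CSD present in the gland". The 70% is then used in "comparing to the systematic sampling TRUS PCa mean detection rate of 30" percent. From this the plan derives 35, 45 and 50 patients for 80%, 90% and 95% power, using a one-sample equivalence test with a 30% margin. It settles on 50 patients plus 10 for early development.

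Selection of Subjects describes the Part 2 population: "We will enroll patients with suspected PCa who are scheduled to undergo an ultrasound fusion-MR prostate biopsy". Background & Significance says of biopsy without good imaging guidance that "only about 25% of tests are positive for cancer" and that "the false negative rates range from 25-45% based on the first-time biopsy". No section gives a cancer prevalence for Part 2 or adjusts the 70% for men without disease.

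**The concern.** The two sides of the comparison have different denominators. The 30% is a rate among men biopsied, with and without cancer. The 79% and 71% come from men whose operation implies that they have cancer.

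- The 71% is conditional on disease. It becomes a rate per enrolled man only when multiplied by the proportion who have disease.
- The 79% is a predictive value by region. It falls once glands without cancer are imaged, because every suspicious region in such a gland is a false positive.

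The 40-point planning effect (70 minus 30), and the power derived from it, therefore do not describe the men the criteria admit. A Part 2 yield well below 70% could be taken as disappointing when it is what the same ARFI performance would produce in this population. Relabelling the 70% as a detection rate, or replacing the equivalence test with a superiority test, would not remove the problem.

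**Working it through.** **1. The plan's own sample sizes.** Alpha is not stated. They can be approximated with n = [SD × (z(1−alpha) + z(1−beta/2)) / gap]², taking one-sided alpha 0.05 (assumed), SD 20 points (one reading of the text) and gap = (70 − 30) − 30 = 10 points. This gives 35, 44 and 52, against the stated 35, 45 and 50. On this reconstruction the 10-point gap comes straight from the 70%, so the sample sizes depend on it.

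**2. Prevalence needed for 70%.** Rate per enrolled man = prevalence × 0.71. Setting this to 0.70 gives prevalence = 0.70/0.71 = 0.986, about 99%.

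**3. Prevalence implied by the protocol's background figures.** Inputs are a positive rate of 25% (Background & Significance) or 30% (the comparator) and a false-negative rate of 25-45% (Background & Significance).

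*Reading A: the false-negative rate is 1 minus sensitivity.* Prevalence = positive rate/(1 − FN).

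| Positive rate | FN | Prevalence | × 0.71 |
|---|---|---|---|
| 25% | 25% | 0.25/0.75 = 33.3% | 23.7% |
| 25% | 45% | 0.25/0.55 = 45.5% | 32.3% |
| 30% | 25% | 0.30/0.75 = 40.0% | 28.4% |
| 30% | 45% | 0.30/0.55 = 54.5% | 38.7% |

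The ARFI rate is 24-39%. In the same men, the ratio of ARFI to systematic detection is 0.71/0.75 = 0.95 to 0.71/0.55 = 1.29, whatever the prevalence. The plan's ratio is 70/30 = 2.33.

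*Reading B: it is the share of negative biopsies that hide cancer.* Prevalence = positive rate + (1 − positive rate) × FN. The lowest value is 0.25 + 0.75 × 0.25 = 43.8% and the highest is 0.30 + 0.70 × 0.45 = 61.5%. Times 0.71, the ARFI rate is 31-44%.

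**4. Enriched prevalence (assumed).** 0.60 × 0.71 = 42.6% and 0.70 × 0.71 = 49.7%.

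**5. Power of 50 men for a rate above 30%.** Exact one-sided binomial test. Reject at 21/50 or more for alpha 0.05 (actual size 0.048) and at 23/50 or more for alpha 0.025 (actual size 0.012; 22/50 just exceeds 0.025).

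| True rate | Power, 0.05 | Power, 0.025 |
|---|---|---|
| 32% | 9% | 3% |
| 39% | 38% | 19% |
| 43% | 61% | 39% |
| 50% | 90% | 76% |

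**6. The grid a revised paragraph could show.** Both margins are assumptions; 85% is an illustrative allowance for several lesions per man and chance hits. Each cell gives the rate, then power at 0.05 / 0.025, from unrounded rates.

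| Prevalence | Sensitivity 71% | Sensitivity 85% |
|---|---|---|
| 40% | 28.4%: 3% / 1% | 34.0%: 15% / 5% |
| 50% | 35.5%: 21% / 8% | 42.5%: 58% / 36% |
| 60% | 42.6%: 59% / 36% | 51.0%: 92% / 80% |
| 70% | 49.7%: 89% / 75% | 59.5%: more than 99% / 98% |

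**7. The comparator under enrichment.** If the 55-75% systematic sensitivity of Reading A held in these men, systematic biopsy would find 0.60 × 0.55 = 33% to 0.60 × 0.75 = 45% at 60% prevalence, and 0.70 × 0.55 = 38.5% to 0.70 × 0.75 = 52.5% at 70%. All of these exceed the fixed 30%.

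**The case against.** **Enrichment.** The background figures describe biopsy without good imaging guidance, whereas Part 2 takes men already scheduled for fusion biopsy, whose prevalence is probably higher. This stands. A reader might infer that the plan's own figures put ARFI close to the 30% comparator, or that Part 2 enrols unselected suspects. The documents support neither, because they give no prevalence for this group.

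**Sign of the gap.** A reader might also infer that ARFI is expected to do worse than systematic biopsy, since 24% is below 30%. That subtracts the 30% comparator from a rate built on the 25% positive rate. Using one rate throughout, the lower end is 23.7 against 25 or 28.4 against 30, a shortfall of 1.3 to 1.6 points. Reading B lies wholly above 30%.

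**Units.** The 71% concerns CSD and appears to be counted by lesion, while the 30% concerns any cancer per man. With up to three targets and two to four cores each, per-man detection of any cancer could exceed 71%. This stands, and it is why sensitivity should be varied rather than fixed at 71%. The 99% in step 2 likewise treats the 70% as a per-man rate although the plan calls it a specificity; the comparison with 30% requires that treatment.

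**Different test.** The powers in steps 5 and 6 come from an exact superiority test at an assumed alpha, and the plan's 95% from an equivalence test on a mean. A reader might conclude that true power is 9% rather than 95%. That contrast is not like for like and is not claimed.

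**Feasibility.** The study's stated purpose is feasibility, recruitment is tied to an existing grant, and nothing makes 70% a success criterion. All true. The plan nevertheless states a hypothesis of a higher detection rate and gives power for it, so its planning value should fit the men enrolled.

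**Conclusion.** The point holds. The 70% is supported only by results in men who can be inferred to have cancer, and it is compared with a rate whose denominator includes men without cancer. The 40-point planning effect is therefore unsupported for the Part 2 population.

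The size is uncertain. At 71% detection the expected rate is 24-39% or 31-44% on the background figures, depending on how the false-negative rate is read, and 43-50% at assumed prevalence of 60-70%. The most favourable corner of the grid, with both inputs assumed, reaches 59.5%. All fall at least 10 points below 70%, and most fall far below it. Power against 30% could be very low or adequate depending on a prevalence the plan does not state. Where prevalence is high enough to give good power, the fixed 30% probably understates what systematic biopsy would find in the same men, so exceeding it would say less about ARFI.

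This rests on three assumptions: that prostatectomy patients have cancer (inferred from the procedure), that 71% can serve as an approximate per-man sensitivity, and one-sided alpha of 0.05 or 0.025.

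**What to change.** In the Part 2 paragraph of Data Analysis & Statistical Considerations:

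- Replace the 70% with an expected per-man cancer detection rate for men with suspected cancer: an assumed prevalence in fusion-scheduled men (for example 40-70%) times an assumed per-man sensitivity (for example 71-85%). Note that the 71% is a CSD figure from men with cancer.
- State alpha, and give the power of the fixed 50 patients over that grid for the stated hypothesis of a rate above 30%.
- Say that enrichment of fusion-scheduled men would also raise the systematic rate above 30%.
- State that the 79% and 71% describe men with cancer and are not the expected Part 2 yield.

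Keep 50 + 10 patients. The cost is one rewritten paragraph, with no added patients or procedures. The downside is a less favourable stated power.

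### Part 2 aims to show a higher detection rate than systematic TRUS, but its test and power come from an equivalence test that cannot show this

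*Combined protocol and SAP*

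**What the plan says.** Everything relevant is in the Part 2 paragraph of Data Analysis & Statistical Considerations.

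- Hypothesis: "we will test the hypothesis that ARFI guided targeted biopsy provides a higher PCa detection rate than that reported for systematic TRUS biopsy".
- Assumed ARFI value: "Assuming an ARFI imaging specificity for CSD of 70"%.
- Reference: "comparing to the systematic sampling TRUS PCa mean detection rate of 30"%, a fixed literature figure.
- Test: "through a one-mean, one-sample equivalence test with a 30% testing margin", with "a standard deviation of up to 20% of the target ARFI imaging specificity".
- Power: "inclusion of 35, 45, and 50 patients would achieve study powers of 80%, 90%, and 95%, respectively".
- Size: 50 patients, "plus 10 initial patients for early phase development and workflow integration", 60 in all.
- Yield of clinically significant disease (CSD) is defined per core: "number of cores containing CSD/total number of cores".

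The protocol gives no null value, centre of the equivalence region, alpha, sidedness or decision rule, and names no other test for the comparison with TRUS.

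**The concern.** The hypothesis is directional and the named test is not. Equivalence testing rejects the null when the estimate is shown to lie inside a band around a reference. The plan's assumed gain is 70 − 30 = 40 points, which is larger than its own 30-point margin. If the band is centred on the TRUS rate, the anticipated benefit lies outside the region that counts as success, and no benefit at all lies at its centre.

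This is the only hypothesis in the protocol with a stated power, and it justifies the Part 2 enrolment. A trial that declared success on this test would have shown only that the ARFI rate is below 60%, which is compatible with no improvement over TRUS.

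**Working it through.** **Inputs.** From the plan: reference 30%, assumed ARFI value 70%, margin 30% (read as 30 points), n = 35, 45, 50. Assumed because not stated: alpha of 5% per side, with 2.5% also tried. Three SDs were used:

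- 14 points, the literal reading (0.20 × 70)
- 20 points, if 20% is meant as an absolute value
- 45.8 points, for a yes/no outcome at 70% (√(0.70 × 0.30) = 0.458)

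**Reproducing 35/45/50.** The standard one-sample equivalence formula is

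`n = [SD × (z(1−α) + z(1−β/2)) / (margin − |difference|)]²`

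With SD 20, α = 0.05, margin 30 and difference 40, the denominator is 30 − 40 = −10:

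- 80%: [20 × (1.645 + 1.282) / −10]² = 34.3, so 35
- 90%: [20 × (1.645 + 1.645) / −10]² = 43.3, so 44
- 95%: [20 × (1.645 + 1.960) / −10]² = 52.0, so 52

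The stated figures are thus met within 2 patients. The formula's powers at 35, 45 and 50 are 81.1%, 91.3% and 94.1%. The match arises only because squaring removes the minus sign. The formula is valid only when the true difference lies inside the margin, and here it does not. The literal SD of 14 gives 17/22/26 and does not match.

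**Reading 1: equivalence around 30% (region 0% to 60%).** Probability of success of two one-sided t-tests at n=50:

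| SD (points) | Alpha per side | True rate 70% | True rate 30% |
|---|---|---|---|
| 14 | 5% | 1.7 × 10⁻¹¹ | about 100% |
| 20 | 5% | 1.4 × 10⁻⁷ | about 100% |
| 45.8 | 5% | 0.08% | 99.6% |
| 45.8 | 2.5% | 0.03% | 99.0% |

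**Reading 2: equivalence around 70% (region 40% to 100%).** This does not test whether ARFI exceeds 30%. It also does not give the stated sizes. At 5% per side, 80/90/95% power needs 4/5/5 patients (SD 14), 6/7/8 (SD 20) or 22/27/32 (SD 45.8).

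**Reading 3: superiority by a margin (H0: mean ≤ 30 + 30 = 60%).** One-sample t-test, true mean 70%, one-sided 2.5%:

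| SD (points) | n=35 | n=45 | n=50 |
|---|---|---|---|
| 20 | 82.0% | 90.7% | 93.4% |
| 14 | 98.4% | 99.7% | 99.9% |

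With SD 20 this is also near 80/90/95%, so the test may simply be mislabelled. But then the word equivalence is wrong, the 60% null appears nowhere, and the SD is not the one written. For a yes/no outcome per patient, exact binomial power at n=50 against 60% is 32.8% (one-sided 5%, reject at 37 or more) or 22.3% (2.5%, reject at 38 or more).

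**A test that fits the hypothesis.** Exact one-sided binomial test of H0: p ≤ 0.30, n=50:

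| One-sided alpha | Reject at | Actual size | Power at 70% | Power at 50% |
|---|---|---|---|---|
| 5% | 21 or more | 4.8% | >99.9% | 90% |
| 2.5% | 23 or more | 1.2% | >99.9% | 76% |

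**The case against.** The equivalence test appears once, as the method behind the power figures. No sentence makes it the decision rule for the final analysis, and the stated aim is still to show a higher rate. On that view the power statement is mis-specified and the final test is missing, but the trial is not committed to rewarding a match with TRUS. This is fair, and it is why the success probabilities above are conditional on a centre of 30% and an assumed alpha. It does not restore the plan: no other test is named, so the stated power still belongs to a procedure that cannot support the hypothesis.

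The origin of 35/45/50 cannot be settled either. A sign lost in the equivalence formula and a mislabelled margin-superiority test both come close, and both need an unstated alpha and an SD of 20 points. A hidden 60% bar is therefore only one possibility.

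The outcome could also be a per-patient fraction of positive cores, since the plan speaks of a mean and an SD and defines yield per core. That stands as a reason for the sponsor to choose the endpoint. The 22–33% power figure applies only to a yes/no outcome against 60%.

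Finally, the stated objective is feasibility and 50 patients are enough. Both are true, but the protocol still promises a hypothesis test with formal power.

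**Conclusion.** The concern holds, and the text must be corrected. The contradiction between a superiority hypothesis and an equivalence test is in the wording and depends on no assumption. Its size depends on the reading. Centred on 30% at n=50, the stated 95% power becomes 0.08% or less, while success when ARFI equals TRUS is 99.0% or more; this holds for all three SDs and for 5% or 2.5% per side. Neither alternative reading supports the text as written. The defect lies in the named test and its power statement, not in the number of patients.

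**What to change.** Delete the equivalence test, the 30% margin and the 80/90/95% powers. Suggested replacement:

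*The per-patient ARFI-targeted detection rate of [PCa or CSD] in the 50 analysis patients will be tested with a one-sided exact binomial test of H0: p ≤ 0.30 at [alpha] and reported with an exact 95% confidence interval. H0 is rejected at [21 or more of 50 if alpha is 5%; 23 or more if alpha is 2.5%].*

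State the power of this test from the last table above. The sponsor should confirm four things:

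1. **Alpha.** One-sided 2.5% agrees with a 95% interval (lower limit 31.8% at 23 of 50). At one-sided 5%, 21 or 22 detections reject H0 although the 95% lower limits are 28.2% and 29.99%, so a 90% interval would match.
2. **Unit.** Per patient, or a core-based fraction. A core-based endpoint needs a one-sided test of its mean against a reference on the same scale, with its own SD and power.
3. **Disease definition.** Either PCa or CSD, for both the ARFI rate and the reference. If CSD is chosen, a TRUS rate for CSD must replace 30% and the cut-off must be recomputed.
4. **Analysis set.** Whether the 10 workflow patients are excluded, as the count of 50 implies but the text does not say.

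If superiority by 30 points was intended, state H0: rate ≤ 60% openly, with its 22–33% power at n=50 for a yes/no outcome.

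The cost is protocol wording and these decisions, best fixed before results are seen. No extra patients or procedures are needed.
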